1.0 Trial Summary

Abbreviated Title	Pembrolizumab for previously treated high grade NETs
Trial Phase	Phase 2
Clinical Indication	Previously treated High Grade Neuroendocrine tumors
Trial Type	Open-label single arm
Type of control	None
Route of administration	Pembrolizumab given intravenously at a fixed dose of 200mg every 3 weeks
Trial Blinding	None
Treatment Groups	Single arm
Number of trial subjects	21
Estimated duration of trial	3.5 years
Duration of Participation	2 years

2.0 Trial Design

[figure not shown]
This is a single-arm, open label phase 2 study exploring monotherapy with the PD-1 antibody pembrolizumab (or MK-3475) given intravenously at a fixed dose of 200mg every 3 weeks for patients with high grade neuroendocrine tumors (except any high grade NETs of large or small cell type of lung/thymus origin and merkel cell carcinoma.), who have received at least 1 prior systemic therapy containing a platinum agent. The primary endpoint of the study is objective response rate. Secondary outcomes are progression free and overall survival and rate of toxicities. Patients will be assessed for response with CT scans every 9 weeks during the first year and every 12 weeks thereafter, using the RECIST 1.1 criteria. Correlative endpoints will be exploratory and assess PD-1 expression on peripheral blood mononuclear cells; peripheral blood NK-cell functional assays; PD-1 and PD-L1 expression on tumor tissue as well as mutational analysis of archived tumor tissue.

Treatment Schema

Screening period (within 28 days)

Metastatic high grade Neuroendocrine tumors Eligibility:

- Histologically confirmed HGNET with Ki67>20%
- Disease progression or recurrence after at least 1 platinum containing chemotherapy regimen
- PS : ECOG 0-1
- Informed consent
- Measurable disease
- Exclude any high grade NETs of large or small cell type of lung/thymus origin, merkel cell carcinoma.

* Pts may be treated beyond first progression under protocol defined circumstances

3.0 Objectives

3.1. Primary Objective

To estimate objective response rate (ORR), using RECIST 1.1, in previously treated metastatic High Grade Neuroendocrine Tumors (HGNET) patients treated with pembrolizumab monotherapy

3.2. Secondary Objectives

- To evaluate progression free survival (PFS) (using RECIST 1.1) in metastatic HGNET patients treated with pembrolizumab monotherapy.
- To evaluate overall survival (OS) in metastatic HGNET patients treated with pembrolizumab monotherapy.
- Incidence of toxicity, graded according to National Cancer Institute Common Toxicity Criteria (NCI-CTC) version 4.0.

3.3. Exploratory objectives

- To correlate biomarkers related to PD-1 blockade in tumor samples (such as TILs, PD-1, PD-L1) with overall response rate, progression free survival, and overall survival
- To characterize molecular and biological profile of tumors that respond to pembrolizumab by performing genomic analysis of tumor samples and by evaluating the expression levels of PD-L1, PD-L2 on tumor cells; PD-L1, PD-1 on TILs and T-regulatory cells (T-regs) in the tumor microenvironment. To compare PD-1 expression and leukocyte activation markers on circulating T-regs pre-treatment, at week 6, and at time of disease progression
- To compare functional responses (degranulation) by NK cells pre-treatment, at week 6, and at end of treatment.

4.0 Introduction

4.1. Study Disease

Neuroendocrine tumors (NETs) consist of a spectrum of malignancies that can arise from neuroendocrine cells throughout the body. They are currently classified as well differentiated (low-grade to intermediate-grade) NETs and poorly differentiated or HGNET based on morphology and the proliferation rate.[1] NETs are rare tumors with an incidence of 3.5-5/100000 per year[2] and HGNETs account for about 10% to 20% of malignant digestive NETs.[3] HGNETs are defined as tumors with poorly differentiated morphology and a higher proliferation rate (Ki67 > 20%) than well differentiated NETs. They are characterized by a high proclivity for metastatic dissemination even among patients with clinically localized tumors.[4] Well and poorly differentiated NETs are grouped together in the general class of NET only because of generic neuroendocrine marker expression (ie, detection of synaptophysin and/or chromogranin by immunohistochemistry).[5]

Recent molecular discoveries have led to therapeutic advances in well differentiated NETs with the approval of targeted therapies like everolimus and sunitinib.[6] In contrast, much less is known about HGNETs, and no prospective studies have evaluated HGNETs originating outside of the lung. These are aggressive carcinomas that typically present at a late stage and have a dismal median overall survival of only 10 months.[2] To date, and even for the current standard of care regimen, no prospective trial has been conducted to guide treatment for this disease and current treatment recommendations are extrapolated from the small cell lung cancer literature.[7] These are generally managed with platinum-based chemotherapy with a modest PFS (4months) and OS (11 months) benefit.[7-11] After firstline treatment, no further standard therapy has been established for HGNETs. No prospective trials have been conducted and a few small, retrospective, studies with chemotherapy (temozolamide, oxaliplatin, taxanes etc.) have quoted a response rate between 0-20% in the second line setting and <5% in the third line setting[11-14]. The responses, however, are of short duration. Data pertaining to histologic classification and tumor biology are also extremely limited making the care of patients with this disease entity a significant challenge. Prospective studies evaluating potential treatment options with associated correlative studies to better understand the histologic and molecular features of these carcinomas are therefore desperately needed.

4.2. Agent under Investigation/intervention

The importance of intact immune surveillance in controlling outgrowth of neoplastic transformation has been known for decades[15]. Accumulating evidence shows a correlation between tumor-infiltrating lymphocytes (TILs) in cancer tissue and favorable prognosis in various malignancies[16-20]. In particular, the presence of CD8+ T-cells and the ratio of CD8+ effector T-cells / FoxP3+ regulatory T-cells seems to correlate with improved prognosis and long-term survival in many solid tumors.

The PD-1 receptor-ligand interaction is a major pathway hijacked by tumors to suppress immune control. The normal function of PD-1, expressed on the cell surface of activated Tcells under healthy conditions, is to down-modulate unwanted or excessive immune responses, including autoimmune reactions. PD-1 (encoded by the gene Pdcd1) is an Ig

superfamily member related to CD28 and CTLA-4 which has been shown to negatively regulate antigen receptor signaling upon engagement of its ligands (PD-L1 and/or PD-L2) [21, 22]. The structure of murine PD-1 has been resolved [23]. PD-1 and family members are type I transmembrane glycoproteins containing an Ig Variable-type (V-type) domain responsible for ligand binding and a cytoplasmic tail which is responsible for the binding of signaling molecules. The cytoplasmic tail of PD-1 contains 2 tyrosine-based signaling motifs, an immunoreceptor tyrosine-based inhibition motif (ITIM) and an immunoreceptor tyrosine based switch motif (ITSM). Following T-cell stimulation, PD-1 recruits the tyrosine phosphatases SHP-1 and SHP-2 to the ITSM motif within its cytoplasmic tail, leading to the dephosphorylation of effector molecules such as CD3ζ, PKCθ and ZAP70 which are involved in the CD3 T-cell signaling cascade [22, 24-26]. The mechanism by which PD-1 down modulates T-cell responses is similar to, but distinct from that of CTLA-4 as both molecules regulate an overlapping set of signaling proteins[27, 28]. PD-1 was shown to be expressed on activated lymphocytes including peripheral CD4+ and CD8+ Tcells, B-cells, T regs and Natural Killer cells[29, 30]. Expression has also been shown during thymic development on CD4-CD8- (double negative) T-cells as well as subsets of macrophages and dendritic cells[31]. The ligands for PD-1 (PD-L1 and PD-L2) are constitutively expressed or can be induced in a variety of cell types, including nonhematopoietic tissues as well as in various tumors[28, 32-34]. Both ligands are type I transmembrane receptors containing both IgV- and IgC-like domains in the extracellular region and contain short cytoplasmic regions with no known signaling motifs. Binding of either PD-1 ligand to PD-1 inhibits Tcell activation triggered through the T-cell receptor. PD-L1 is expressed at low levels on various non-hematopoietic tissues, most notably on vascular endothelium, whereas PD-L2 protein is only detectably expressed on antigenpresenting cells found in lymphoid tissue or chronic inflammatory environments. PD-L2 is thought to control immune T-cell activation in lymphoid organs, whereas PD-L1 serves to dampen unwarranted T-cell function in peripheral tissues[28]. Although healthy organs express little (if any) PD-L1, a variety of cancers were demonstrated to express abundant levels of this T-cell inhibitor. PD-1 has been suggested to regulate tumor-specific T-cell expansion in subjects with renal cell carcinoma[35]. This suggests that the PD-1/PD-L1 pathway plays a critical role in tumor immune evasion and should be considered as an attractive target for therapeutic intervention. Pembrolizumab (MK-3475), previously known as SCH 900475, is a potent and highly selective humanized monoclonal antibody (mAb) of the IgG4/kappa isotype designed to directly block the interaction between PD-1 and its ligands, PD-L1 and PD-L2.

4.3. Pre-clinical and Clinical Trials:

Refer to the Investigator's Brochure for Preclinical and Clinical data.

4.4. Study Rationale

Immune checkpoint blockade is a rapidly advancing therapeutic approach in the field of immuno-oncology and treatment with investigational agents targeting this mechanism has induced regressions in several types of cancer. These agents are tolerable and adverse effects (AEs) are generally manageable in patients. They have shown activity in wide range of

malignancies including melanoma, renal cell carcinoma and lung cancer, and more data is emerging by the day.[36-38] No published studies have evaluated PD-L1 expression in high grade NET. In SCLC, PD-L1 expression on tumor cells is reported to be low (0-27%) but 18.5% show PD-L1 expression in tumor-infiltrating macrophages and 48% harbor PD-1 positive lymphocytes.[39, 40] Immune checkpoint blockers have not been studied in NETs but are being actively investigated in SCLC and Merkel Cell Carcinoma with promising results. In a recently reported interim analysis of a study using Nivolumab+/- Ipilimumab in pretreated advanced small cell lung cancer, researchers reported a partial response in 15% and stable disease (SD) in 22.5% patients. In the combination arm, complete response was seen in 5%, partial response in 20% and stable disease in 30% patients.[41] In the KEYNOTE-028 study, rate of PD-L1 positivity in small cell lung cancer was found to be around 27%. In the cohort of 17 evaluable patients treated with pembrolizumab, there were no treatment-related deaths or discontinuations due to AEs. 25% patients had a partial response and 7% had stable disease, resulting in a disease control rate of 31%.[40] (NCT02054806) In the initial phase I study of Pembrolizumab, a patient with Merkel cell carcinoma experienced complete responses of 56+ weeks' duration[42]. This led to the phase II study in advanced merkel cell carcinoma where the objective response rate with pembrolizumab was 71%, which included a complete response in 2 of 14 patients[43]. The drug is currently being investigated as a first line therapy for patients with locally advanced/metastatic merkel cell carcinoma. (NCT02267603). Both these tumor types (small cell lung cancer and merkel cell carcinoma) are thought to be of neuroendocrine lineage and are treated similarly with frontline platinum/etoposide combinations, just like other high grade neuroendocrine carcinomas. The impressive activity of pembrolizumab in these tumors, presents a strong argument for investigating its role in HGNETs.

Snyder et.al.described the importance of tumor genetics in defining the basis of the clinical benefit from checkpoint blockade. In their study, mutational load correlated with improved overall survival and response to immunotherapy[44]. Preliminary data from our in-house IRB approved study, that utilized an NGS platform to detect somatic mutations in 50 cancer-related genes on archived tissue, found a staggering 77% (16/21) rate of mutations in the HGNETs with 44% of the tumors having more than one mutation (on the limited 50 gene panel). We enrolled 21 patients with HGNETs over 15 months in this study.[45] This provides another rationale for testing pembrolizumab in HGNETs.

As discussed in section 4.1, after first-line treatment, no further standard therapy has been established for HGNETs. Several small, retrospective, studies with chemotherapy (temozolamide, oxaliplatin, taxanes etc.) have quoted short lived responses after the first line setting.

In summary, the lack of second line treatment options for HGNETs highlights the unmet need for drug development in this rare tumor type. The higher mutational load exhibited by HGNETs and promising activity of checkpoint blockers in small cell lung cancer and merkel cell carcinoma provide strong rationale for studying pembrolizumab, a highly selective, humanized monoclonal antibody against PD-1, in HGNETs with respect to efficacy and toxicity. Therefore, we propose a phase II, open-label study of pembrolizumab monotherapy in patients with metastatic HGNETs who have progressed on at least one platinum containing regimen.

We hypothesize that administration of pembrolizumab to patients with metastatic HGNETs will result in a clinically meaningful response rate and that it will have an acceptable safety profile when given as a single agent to patients with metastatic, HGNETs.

4.5. Rationale for Dose Selection/Regimen/Modification

Previously, an open-label Phase I trial (NCT01848834) was conducted to evaluate the safety and clinical activity of single agent Pembrolizumab (MK-3475). The dose escalation portion of the trial evaluated three dose levels, 1 mg/kg, 3 mg/kg, and 10 mg/kg, administered every 2 weeks (Q2W) in subjects with advanced solid tumors. All three dose levels were well tolerated and no dose-limiting toxicities were observed. This first in human study of pembrolizumab showed evidence of target engagement and objective evidence of tumor size reduction at all dose levels (1 mg/kg, 3 mg/kg and 10 mg/kg Q2W). No MTD has been identified to date. Recent data from other clinical studies within the pembrolizumab program has shown that a lower dose of pembrolizumab and a less frequent schedule may be sufficient for target engagement and clinical activity.

PK data analysis of pembrolizumab administered Q2W and Q3W showed slow systemic clearance, limited volume of distribution, and a long half-life (refer to IB). Pharmacodynamic data (IL-2 release assay) suggested that peripheral target engagement is durable (>21 days). This early PK and pharmacodynamic data provides scientific rationale for testing a Q2W and Q3W dosing schedule.

A population pharmacokinetic analysis has been performed using serum concentration time data from 476 patients. Within the resulting population PK model, clearance and volume parameters of pembrolizumab were found to be dependent on body weight. The relationship between clearance and body weight, with an allometric exponent of 0.59, is within the range observed for other antibodies and would support both body weight normalized dosing or a fixed dose across all body weights. Pembrolizumab has been found to have a wide therapeutic range based on the melanoma indication. The differences in exposure for a 200 mg fixed dose regimen relative to a 2 mg/kg Q3W body weight based regimen are anticipated to remain well within the established exposure margins of 0.5 - 5.0 for pembrolizumab in the melanoma at 10 mg/kg Q3W vs. the proposed dose regimen of 2 mg/kg Q3W (i.e. 5-fold higher dose and exposure). The population PK evaluation revealed that there was no significant impact of tumor burden on exposure. In addition, exposure was similar between the NSCLC and melanoma indications. Therefore, there are no anticipated changes in exposure between different indication settings.

The rationale for further exploration of 2 mg/kg and comparable doses of Pembrolizumab in solid tumors was based on: 1) similar efficacy and safety of Pembrolizumab when dosed at either 2 mg/kg or 10 mg/kg Q3W in melanoma patients, 2) the flat exposure-response relationships of Pembrolizumab for both efficacy and safety in the dose ranges of 2 mg/kg Q3W to 10 mg/kg Q3W, 3) the lack of effect of tumor burden or indication on distribution

behavior of Pembrolizumab (as assessed by the population PK model) and 4) the assumption that the dynamics of Pembrolizumab target engagement will not vary meaningfully with tumor type.

The choice of the 200 mg Q3W as an appropriate dose for the switch to fixed dosing is based on simulations performed using the population PK model of Pembrolizumab showing that the fixed dose of 200 mg every 3 weeks will provide exposures that 1) are optimally consistent with those obtained with the 2 mg/kg dose every 3 weeks, 2) will maintain individual patient exposures in the exposure range established in melanoma as associated with maximal efficacy response and 3) will maintain individual patients exposure in the exposure range established in melanoma that are well tolerated and safe.

A fixed dose regimen will simplify the dosing regimen to be more convenient for physicians and to reduce potential for dosing errors. A fixed dosing scheme will also reduce complexity in the logistical chain at treatment facilities and reduce wastage.

4.6. Rationale for endpoints

4.6.1. Primary endpoint

The primary efficacy objective of this trial is to evaluate the anti-tumor activity of pembrolizumab (MK-3475) (200 mg Q3W) monotherapy in subjects with previously treated metastatic high grade neuroendocrine tumors. Objective response rate (ORR) based on RECIST 1.1 will be used as the primary efficacy endpoint. Secondary endpoints in this study is progression free survival (per RECIST 1.1), and overall survival.

4.6.2. Safety Endpoint

The safety endpoint in this study is to characterize the safety and tolerability of Pembrolizumab in patients with previously treated metastatic high grade neuroendocrine tumors. Adverse events and laboratory test values observed in this study are also safety endpoints. The primary safety analysis will be based on subjects who experienced toxicities requiring discontinuation of therapy as defined by the protocol (section 7.0). Safety will be assessed by quantifying the toxicities and grades experienced by subjects who have received pembrolizumab (MK-3475), including serious adverse events (SAEs) and events of clinical interest (ECIs). Safety will be assessed by reported adverse experiences using CTCAE, Version 4.0. The attribution to drug, time-of-onset, duration of the event, its resolution, and any concomitant medications administered will be recorded. AEs will be analyzed including but not limited to all AEs, SAEs, fatal AEs, and laboratory changes. Furthermore, specific immune-related adverse events (irAEs) will be collected and designated as immune-related events of clinical interest (ECIs) as described in Section 9.1.7.

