6.4. Concomitant Medications, Supportive Care, Excluded Therapies and Restrictions

Medications or vaccinations specifically prohibited in the exclusion criteria are not allowed during the ongoing trial. If there is a clinical indication for any medication or vaccination specifically prohibited during the trial, discontinuation from trial therapy or vaccination may be required. The final decision on any supportive therapy or vaccination rests with the investigator and/or the subject's primary physician.

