6.4.2. Prohibited Concomitant Medications

Subjects are prohibited from receiving the following therapies during the Screening and Treatment Phase of this trial:

- Antineoplastic systemic chemotherapy or biological therapy
- Immunotherapy not specified in this protocol
- Chemotherapy not specified in this protocol
- Investigational agents other than pembrolizumab
- Radiation therapy

Note: Radiation therapy to a symptomatic solitary lesion or to the brain may be allowed at the investigator's discretion.

- Live vaccines within 30 days prior to the first dose of trial treatment and while participating in the trial. Examples of live vaccines include, but are not limited to, the following: measles, mumps, rubella, varicella/zoster, yellow fever, rabies, BCG, and typhoid vaccine.
- Systemic glucocorticoids for any purpose other than to modulate symptoms from an event of clinical interest of suspected immunologic etiology. The use of physiologic doses of corticosteroids may be approved after consultation with the Sponsor.

Subjects who, in the assessment by the investigator, require the use of any of the aforementioned treatments for clinical management should be removed from the trial. Subjects may receive other medications that the investigator deems to be medically necessary.

The Exclusion Criteria describes other medications which are prohibited in this trial.

There are no prohibited therapies during the Post-Treatment Follow-up Phase

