6.4.3. Rescue Medications & Supportive Care

Subjects should receive appropriate supportive care measures as deemed necessary by the treating investigator. Suggested supportive care measures for the management of adverse events with potential immunologic etiology are outlined below and in greater detail in appendix (section 17.3). Where appropriate, these guidelines include the use of oral or intravenous treatment with corticosteroids as well as additional anti-inflammatory agents if symptoms do not improve with administration of corticosteroids. Note that several courses of steroid tapering may be necessary as symptoms may worsen when the steroid dose is decreased. For each disorder, attempts should be made to rule out other causes such as metastatic disease or bacterial or viral infection, which might require additional supportive care. The treatment guidelines are intended to be applied when the investigator determines the events to be related to Pembrolizumab.

Note: if after the evaluation the event is determined not to be related, the investigator may follow the AE reporting guidance but does not need to follow the treatment guidance (as outlined in appendix 17.3). Refer to section 7.0 for dose modification.

It may be necessary to perform conditional procedures such as bronchoscopy, endoscopy, or skin photography as part of evaluation of the event. Suggested conditional procedures, as appropriate, can be found in the ECI guidance document.

Pneumonitis:

- For **Grade 2 events**, treat with systemic corticosteroids. When symptoms improve to Grade 1 or less, steroid taper should be started and continued over no less than 4 weeks.
- For Grade 3-4 events, immediately treat with intravenous steroids. Administer additional anti-inflammatory measures, as needed.
- Add prophylactic antibiotics for opportunistic infections in the case of prolonged steroid administration.

Diarrhea/Colitis:

Subjects should be carefully monitored for signs and symptoms of enterocolitis (such as diarrhea, abdominal pain, blood or mucus in stool, with or without fever) and of bowel perforation (such as peritoneal signs and ileus).

- All subjects who experience diarrhea/colitis should be advised to drink liberal quantities of clear fluids. If sufficient oral fluid intake is not feasible, fluid and electrolytes should be substituted via IV infusion. For Grade 2 or higher diarrhea, consider GI consultation and endoscopy to confirm or rule out colitis.

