7.0 Dose Modifications

7.1. General Principles

Dose modifications will be made based only on the guidelines described in Section 7.0. Patients requiring treatment to be held > 42 days for recovery from toxicity must discontinue protocol treatment. Adverse events (both non-serious and serious) associated with Pembrolizumab exposure may represent an immunologic etiology. These adverse events may occur shortly after the first dose or several months after the last dose of treatment. Pembrolizumab must be withheld for drug-related toxicities and severe or life-threatening AEs as per Table 3 below. See Section 6.4 (Supportive Care Guidelines), Table 2 and

Appendix 17.3 for supportive care guidelines, including use of corticosteroids. For subjects whose dose interval was increased due to toxicity, subjects may resume Pembrolizumab upon resolution of toxicity to Grade 0-1 or baseline. This dose would be considered Day 1 of the next cycle and should be in alignment with the new schedule

Toxicity	Hold Treatment For Grade	Timing for Restarting Treatment	Discontinue Subject if
Diarrhea/Colitis	2-3	Toxicity resolves to Grade 0-1.	Toxicity does not resolve to grade 0-1 within 6 weeks of last dose or inability to reduce corticosteroid to 10 mg or less of prednisone or equivalent per day within 12 weeks.
	4	Permanently discontinue	Permanently discontinue
AST, ALT, or	2-3	Toxicity resolves to Grade 0-1	Toxicity does not resolve to grade 0-1 within 6 weeks of last dose.
Increased Bilirubin	4	Permanently discontinue	Permanently discontinue
Type 1 diabetes mellitus (if new onset) or Hyperglycemia	T1DM or 3-4	Hold Pembrolizumab for new onset Type 1 diabetes mellitus or Grade 3- 4 hyperglycemia associated with evidence of beta cell failure.	Resume Pembrolizumab when patients are clinically and metabolically stable.
Hypophysitis	2-3	Toxicity resolves to Grade 0-1	Toxicity does not resolve to grade 0-1 within 6 weeks of last dose or inability to reduce corticosteroid to 10 mg or less of prednisone or equivalent per day within 12 weeks.
	4	Permanently discontinue	Permanently discontinue
Hyperthyroidism	3	Toxicity resolves to Grade 0-1	Toxicity does not resolve to grade 0-1 within 6 weeks of last dose or inability to reduce corticosteroid to 10 mg or less of prednisone or equivalent per day within 12 weeks.
	4	Permanently discontinue	Permanently discontinue

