Hypothyroidism		Therapy with Pembrolizumab can be continued while treatment for the thyroid disorder is instituted	Therapy with Pembrolizumab can be continued while treatment for the thyroid disorder is instituted.
Infusion Reaction	3-4	Permanently discontinue	Permanently discontinue

Table 3. Dose Modification Guidelines for Pembrolizumab-Related Adverse Events

Toxicity	Hold Treatment For Grade	Timing for Restarting Treatment	Discontinue Subject if	
Pneumonitis	2	Toxicity resolves to Grade 0-1	xicity resolves to Grade 0-1 Toxicity does not resolve to grade 0-1 within 6 weeks of last dose or inability to reduce corticosteroid to 10 mg or less of prednisone or equivalent per day within 12 weeks.	
	3-4	Permanently discontinue	Permanently discontinue	
Renal Failure or Nephritis	2	Toxicity resolves to Grade 0-1	-1 Toxicity does not resolveto grade 0-1 within 6 weeks of last dose -1 or inability to reduce corticosteroid to 10 mg or less of prednisone or equivalent per day within 12 weeks.	
	3-4	Permanently discontinue	Permanently discontinue	
All Other Drug- Related	3 or Severe	Toxicity resolves to Grade 0-1	Toxicity does not resolve to grade 0-1 within 6 weeks of last dose or inability to reduce corticosteroid to 10 mg or less of prednisone or equivalent per day within 12 weeks.	
Toxicity ^{1,2}	4	Permanently discontinue	Permanently discontinue	

Note: Permanently discontinue for persistent grade 2 or 3 adverse reactions (excluding endocrinopathies controlled with hormone

replacement therapy) that do not recover to Grade 0-1 within 6 weeks after last dose of Pembrolizumab

¹ Pembrolizumab-specific exclusions to grade 3 non-hematologic toxicity as DLT include:

- Grade 3 rash in the absence of desquamation, no mucosal involvement, does not require steroids, and resolves to Grade
 1 by the next scheduled dose of pembrolizumab.
- 2. Transient Grade 3 AST or ALT elevation, defined as no more than 3 days with or without steroid use

² Pembrolizumab-specific DLT: Episcleritis, uveitis, or iritis of Grade 2 or higher

Dosing interruptions are permitted in the case of medical / surgical events or logistical reasons not related to study therapy (e.g., elective surgery, unrelated medical events, patient vacation, and/or holidays). Subjects should be placed back on study therapy within 6 weeks of the scheduled interruption, unless otherwise discussed with the PI. The reason for interruption should be documented in the patient's study record.

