Adverse events will be assessed continuously throughout the study. If 6 of the first 12 patients have to discontinue study treatment due to treatment related adverse events the study will be interrupted for consideration of dose reduction or termination. If ever 8 of the 21 eligible patients have to discontinue study treatment due to treatment related adverse events the study will be suspended and early termination for excess toxicity will be considered after careful investigation of the causes of the higher than expected toxicities. Once the root of the higher than anticipated toxicities has been determined, the study team will confer with the FCCC DSMC and IRB to make a determination whether accrual can be resumed or the study will be terminated early. The chance of early termination with a true toxicity of 50% is 61%. The chance of study termination under the null of 20% true toxicity is 2.7% and is 83% if true toxicity is 50%.

As discussed earlier, no second line therapies have been prospectively evaluated in high grade neuroendocrine carcinomas and small retrospective studies have shown dismal results with chemotherapy [11-13]. Hence we decided to proceed without a definite stopping rule for futility, given minimal if any, harm associated with ineffective therapy to study participants.]

Correlative studies: Due to this limited sample size, all exploratory analyses of associations of biomarkers with outcomes and changes in marker levels pre- and during treatment will be largely descriptive in nature.

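### Does the pointer to a missing Section 9.1.7 leave the toxicity stopping count open?

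*Combined protocol and SAP*

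**What the plan says.** - **4.6.2 (Safety Endpoint):** specific irAEs are collected and "designated as immune-related events of clinical interest (ECIs) as described in Section 9.1.7". The same section ties the primary safety analysis to discontinuations defined in Section 7.0.
- **9.1.6 (Events of Clinical Interest):** two items, an overdose without symptoms or abnormal laboratory results and a combined AST/ALT, bilirubin and alkaline phosphatase criterion. There is no 9.1.7 in the contents or the body.
- **6.4.2:** the prohibited list has "Systemic glucocorticoids for any purpose other than to modulate symptoms from an event of clinical interest of suspected immunologic etiology". Subjects who "require the use of any of the aforementioned treatments for clinical management should be removed from the trial". The parent section, 6.4, is softer: "discontinuation from trial therapy or vaccination may be required".
- **6.4.3:** directs steroids for several irAEs. For Grade 2 pneumonitis, for example: "treat with systemic corticosteroids. When symptoms improve to Grade 1 or less, steroid taper should be started".
- **7.1 and Table 3:** "Dose modifications will be made based only on the guidelines described in Section 7.0". Many rows allow restart at Grade 0-1, and most of these stop the patient on steroid grounds only for "inability to reduce corticosteroid to 10 mg or less of prednisone or equivalent per day within 12 weeks".
- **13.1:** "If 6 of the first 12 patients have to discontinue study treatment due to treatment related adverse events", the study is interrupted; at 8 of 21 it is suspended.
- **9.2.3 and 9.2.5:** ECIs go from site to sponsor within 24 hours and from sponsor to manufacturer within 2 working days.

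**The concern.** The pointer leads nowhere, and renumbering it to 9.1.6 does not supply the missing content. The term it should define is used elsewhere. If ECI means only the two items in 9.1.6, a patient given steroids for, say, Grade 2 colitis falls outside the exception in 6.4.2 and should leave the trial, while Table 3 would let the same patient restart. A removal of that kind might count toward the stopping rule, whose wording does not cite Section 7.0, but not toward the primary safety analysis, which does. If instead every suspected immune event is an ECI, the treatment sections agree, but mild events become 24-hour reports.

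At stake would be the counted event in the trial's only numerical early-stopping rule, and the expedited reporting load. A side issue was whether 6.4.1 and 8.1.4 disagree on recording medication after day 30.

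**Working it through.** **1. The plan's own figures.** Inputs from 13.1: boundaries 6 of 12 and 8 of 21; toxicity rates 20% and 50%. With X12 and X21 the binomial counts among the first 12 and all 21 patients:

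- P(X12 ≥ 6 | 0.50) = 2510/4096 = 0.613. The plan says 61%, so this reproduces.
- P(X12 ≥ 6 or X21 ≥ 8) = P(X12 ≥ 6) + P(X12 ≤ 5 and X21 ≥ 8). At 20%: 0.0194 + 0.0309 = 0.0503. At 50%: 0.6128 + 0.2974 = 0.9102.
- The plan prints 2.7% and 83%. Those match a second boundary of 9 of 21 (0.0274 and 0.8326). That is a separate matter; both versions are carried below.

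**2. How many situations the closed reading would touch.** Cells where 6.4.3 directs steroids and Table 3 allows restart: pneumonitis G2; diarrhea/colitis G2 and G3; hypophysitis G2 and G3; hyperthyroidism G3; hepatic G2 and G3; renal G2. That is 1 + 2 + 2 + 1 + 2 + 1 = 9. The liver criterion in 9.1.6 can cover only the two hepatic cells, and only when its three laboratory conditions hold together, so 9 − 2 = 7 fall outside the list.

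**3. What the closed reading would do to the rule.** Expected count at 20%: 21 × 0.20 = 4.2, which is 8 − 4.2 = 3.8 patients below the boundary. The documents give no irAE or steroid-use rate, so any increment is an assumption. Take 5 points (21 × 0.05 = 1.05 patients) and 10 points (21 × 0.10 = 2.1 patients):

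| Rate counted | 6/12 or 8/21 | 6/12 or 9/21 |
|---|---|---|
| 20% | 5.0% | 2.7% |
| 25% | 14.3% | 8.4% |
| 30% | 29.4% | 19.0% |

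The arithmetic is sound, but it applies only if the closed reading is right and a 6.4.2 removal counts as a treatment-related discontinuation.

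**4. Is the closed reading right?** The sections side by side:

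- 4.6.2 states outright that specific irAEs are ECIs.
- 8.2.1 asks whether an adverse event may be an ECI of immune origin and gives irAE as its short name.
- The exception in 6.4.2 presupposes ECIs of immune origin. On the closed list it would be almost empty: the overdose item has no symptoms to treat, which leaves only the liver criterion.
- 9.1.6 introduces its items with *include*, which need not be exhaustive.
- 6.4.3, which directs steroids, sits inside the same Section 6.4, and 7.1 refers to Section 6.4 for steroid use.

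**5. Would a 6.4.2 removal be counted?** Section 6.6 lists the mandatory reasons for discontinuation. Its toxicity reason refers to Section 7.0, and needing a prohibited medicine is not a listed reason. Sections 4.6.2 and 7.1 also point to Section 7.0. An analyst who counts toxicity discontinuations by Section 7.0 obtains one set of patients for both the rule and the safety analysis.

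**6. Medication recording.** Section 6.4.1 narrows recording after day 30 to SAEs and ECIs. In 8.1.4 the sentence on concomitant medication is followed by one on medicines related to reportable SAEs and ECIs. Both calendars mark medication review at the 30-day visit and not at 120 days. These agree.

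**The case for a change.** The best case for acting is that 4.6.2 speaks of specific irAEs, which implies a list, and no supplied section contains one. The removal sentence in 6.4.2 is firmer than the wording in 6.4. The stopping rule does not name Section 7.0, and 6.6 also allows an investigator's decision as a reason, so a literal reader could remove and count a steroid-treated patient. With 21 patients, one or two reclassifications matter, and the correction is only wording.

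Part of this stands. The pointer is wrong, and the supplied text does not settle which non-serious irAEs need a 24-hour report. Two documents that may hold the list are cited but were not available here: the ECI guidance document named in 6.4.3 and the separate PDF for Appendix 17.3. Their absence here does not show that the plan lacks the list.

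The stopping-rule argument does not stand. It needs the closed reading, a literal removal under 6.4.2 in preference to Table 3, and a decision to count that removal. Even then a boundary leads to interruption or suspension, not automatic termination. At 8 of 21 the causes are investigated and the monitoring committee and IRB are consulted, so removals caused by a steroid rule could be identified. Nor are the closed list and every immune event the only two choices; a defined list kept in a companion document fits the word *specific* better than either.

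**Conclusion.** No change to the design or analysis follows. This is a wrong section number together with detail that the cited companion documents may supply. On the reading the text supports, no patient moves in or out of the stopping count, and the increases to 14.3% and 29.4% (8.4% and 19.0% with 9 of 21) do not arise. The response-rate definition does not use ECI status. All adverse events are recorded to 120 days, serious irAEs are already 24-hour reports, and 9.2.2 sends reporting doubts to the Study Monitor for confirmation with the Sponsor Investigator.

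The residue is the expedited reporting of non-serious irAEs, which cannot be sized because the documents give no event rate. The ECI wording in 4.6.2, 6.4.2, 8.2.1 and 9.1.6 remains for the sponsor to reconcile as a clerical matter, including what the list contains.

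The conclusion assumes that 9.1.6 is not a closed list and that toxicity discontinuations are counted by Section 7.0. Both are readings of the wording, not views on how patients should be managed.
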